## **Abstract**

**Background:** This study argues that providing evidence-based occupational therapy patient education is vital in order to optimize rehabilitation outcomes. The planned trial aims to evaluate the SADL-eM intervention for people with SCI compared with standard treatment.

**Methods/Design:** This is a parallel randomized clinical trial with two study arms, intervention and control. Ninety patients treated in inpatient rehabilitation settings will be randomly allocated to two study groups. Both groups will receive standard care. The intervention group will also receive a copy of the SADL-eM from their treating occupational therapist during an individual session. Assessment on admission (baseline measure) and after six weeks of admission will use the SCIM-SR as the primary outcome measure. Secondary outcomes include the SCIM-III, Private Religiousness Practices Scale, Organizational Religiousness Short-Form, additional domains of ADL covered by the educational manual and adherence to intervention. Effect will be determined using repeated measures ANOVA.

**Discussion:** The SADL-eM is a comprehensive ADL educational tool that aims to optimize rehabilitation outcomes for people with SCI. If the SADL-eM is demonstrated as clinically effective, this will have significant implications for occupational therapy interventions in LMIC settings.

**Trial registration:** BLINDED FOR REVIEW (Project ID: 1635, HREC Reference number: S17/10/206). Helsinki Committee for Ethical Approval (PHRC/HC/689/20)

**Date of registration:** 30/11/2017, Renewed 12/06/2020

**Keywords:** Occupational therapy, educational intervention, Activities of daily living, Spinal Cord Injury, clinical trials

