### **Research question**

Does the implementation of a SADL-eM delivered to SCI patients in an inpatient rehabilitation setting in the Gaza Strip have a significant impact on activities of daily living?

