### **Primary objectives**

- a. To describe the characteristics of the participants (people with SCI in the Gaza Strip using the Biographical Data Form developed for this study).
- b. To compare the effect of the educational manual, relative to usual care, on self-reported changes in activities of daily living from admission to 6-weeks post-admission, using the SCIM-SR patient-rated measure.
- c. To compare the effect of the educational manual, relative to usual care, on observed changes in activities of daily living from admission to 6-weeks post-admission, using the SCIM-III clinician-rated measure.
- d. To compare the effect of the education manual, relative to usual care, on religious practice using the Private Religiousness Practices Scale and Organizational Religiousness Short-Form.

- e. To compare the effect of the education manual, relative to usual care, on the domains of ADL covered by the education manual including driving and community mobility, personal device care, health management and maintenance, Wudu, and Salat, using questions developed for this research.

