### **Research Hypothesis**

- a. **Null hypothesis:** There is no difference between the SADL-eM and the standard care delivered to inpatients with SCI in a rehabilitation setting.
- b. **Alternative hypothesis:** The implementation of a SADL-eM delivered to inpatients with SCI in a rehabilitation setting has a significant impact on their ADL.

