## **Data Analysis**

Captured data will be coded and reviewed by the researchers for clarity and completion. A spread sheet will be prepared by the three researchers and then loaded to IBMSPSS 21 for analysis. The first author will perform data entry. The research assistant will check the data entry using the original forms, and the research supervisor will check the data for missing data and entry errors.

The following statistical methods will be used to test the research hypothesis:

- a. To describe participants' characteristics: descriptive statistics such as frequency, percentage, mean with standard deviation for Normally distributed data and median and Inter Quartile range will be used for continuous variables that are not Normally distributed will be used.
- b. Missing values will not be substituted. Intention-to treat analysis method will be used for analysis.
- c. To determine the significance of biographical variables at baseline: McNemar and Chi Square with Nominal variables, T-test and Mann-Whitney for interval variables will be used.
- d. To compare the efficacy of the educational manual: Repeated Measures ANOVA/ Linear Mixed Models will be used will be used to assess differences between intervention and control group using the ADL data. The Repeated Measures ANOVA and Linear Mixed Models will be used to analyze the data. Linear Mixed Models has advantage in dealing with missing values and provides fixed and random effect (Krueger and Tian, 2004).
- e. Adherence to the intervention will be summarized using frequency and percentage.

All the data collected and entered (hardcopy and soft copy) will be securely stored by the first researcher in a locked cabinet on hospital premises (hardcopy) and in a password-protected file online.

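### No single SCIM-SR test is named as deciding the trial: the primary outcome, the ANOVA term and the model are all left open, so the 5% error is not protected

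*Combined protocol and SAP*

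**What the plan says.** **Outcome.** The Abstract says assessments "will use the SCIM-SR as the primary outcome measure", and continues: "Secondary outcomes include the SCIM-III, Private Religiousness Practices Scale, Organizational Religiousness Short-Form", followed by the additional ADL domains and adherence. The Primary objectives section puts the same measures under one heading: SCIM-SR (b), SCIM-III (c, "on observed changes in activities of daily living from admission to 6-weeks post-admission, using the SCIM-III clinician-rated measure"), the two religiousness scales (d) and five ADL domains (e). The Secondary objectives cover only biographical predictors and adherence.

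**Hypothesis.** The Research question asks whether the manual will "in the Gaza Strip have a significant impact on activities of daily living", with no measure named. The null reads "There is no difference between the SADL-eM and the standard care delivered to inpatients with SCI in a rehabilitation setting", with no outcome at all. The alternative reads "The implementation of a SADL-eM delivered to inpatients with SCI in a rehabilitation setting has a significant impact on their ADL", again with no measure. Data Collection lists every tool, the religiousness scales included, as part of collecting ADL data, and says these data will serve to test the hypothesis.

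**Analysis.** The Abstract says "Effect will be determined using repeated measures ANOVA". Data Analysis item d says "Repeated Measures ANOVA/ Linear Mixed Models will be used will be used to assess differences between intervention and control group using the ADL data", and its next sentence says both models will be used. It does not say which outcome, term or model decides. The sample size paragraph (90 participants, 45 per arm, a 15% effect size, 80% power) names no outcome or term either.

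**The concern.** The trial has one confirmatory claim, rejection of the null, but several results could be put forward as establishing it. SCIM-SR and SCIM-III both measure ADL and both sit under the primary objectives. A two-group, two-visit repeated measures ANOVA gives two between-arm tests for each outcome: the group main effect and the group-by-time interaction. The wording of item d, a difference between groups, can be read literally as the group term; objectives b and c, which speak of change from admission, point to group-by-time. Without a rule, the choice could be made after the data are seen, and a later reader could not tell a planned result from a selected one.

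The choice of term also affects power. The group term averages in the admission score, taken before the manual is given, when randomised arms should not differ.

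**Working it through.** **Inputs from the documents:** 45 per arm, two visits (admission and 6 weeks), 5% level, 80% power. **Assumed, because the documents do not give them:** two-sided tests, the correlation r between test statistics on different outcomes, the correlation ρ between baseline and week 6, and the SDs at each visit.

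**1. The plan's own figure.** The noncentrality for group-by-time is λ = f²·N·m/(1 − ρ), with m = 2 visits and 1 and N − 2 degrees of freedom. Reading the 15% as Cohen's f = 0.15 with ρ = 0.5:
- N = 90: λ = 0.0225 × 90 × 2 / 0.5 = 8.1, power 80.4%.
- N = 88: power 79.5%.

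So 90 is reproduced exactly as a group-by-time calculation, but only with an effect metric, a ρ and a term that the plan does not state. At the same f and ρ the group term would need N = 264, and has 37% power at 90.

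**2. False rejection when either SCIM measure may count, one term.** For k two-sided 5% tests with common correlation r, the chance that at least one rejects is 1 − P(all |Z| < 1.96). At r = 0 this is 1 − 0.95^k; otherwise it is found by numerical integration.

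| r | 2 measures, 1 term | 2 measures, 2 terms | 4 scales, 1 term |
|---|---|---|---|
| 0 | 9.75% | 18.55% | 18.55% |
| 0.5 | 9.07% | 17.33% | 15.58% |
| 0.7 | 8.35% | 15.99% | 13.04% |
| 0.9 | 7.04% | 13.58% | 9.36% |

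The middle column is 1 − (1 − p₂)², where p₂ is the first column. It assumes equal SDs, so that the two terms are independent (step 3). The last column adds the two religiousness scales, as the Data Collection wording allows. If only the SCIM pair correlates, at 0.7, it is 1 − (1 − 0.0835) × 0.95² = 17.28%.

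**3. False rejection on SCIM-SR alone when either term may count.** With visit SDs s₁ and s₂, the mean of the two visits and the change have correlation
(s₂² − s₁²) / √[(s₁² + s₂²)² − 4ρ²s₁²s₂²].
- Equal SDs: correlation 0 at any ρ, so 1 − 0.95² = 9.75%. Simulation with 200,000 trials at 45 per arm gave 9.66% to 9.78%.
- Week-6 SD 1.5 times baseline: correlations 0.400, 0.434, 0.504 and 0.691 at ρ = 0.3, 0.5, 0.7 and 0.9, giving 9.32%, 9.25%, 9.06% and 8.39%.

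**4. Power at 45 per arm (noncentral t, equal SDs).** Fix the effect at d = 0.6 SDs of change, which group-by-time detects with 80.4%. In SDs of a single score that effect is δ = 0.6·√[2(1 − ρ)]. The standardised effects are then:
- group term: (δ/2) / √[(1 + ρ)/2] = 0.6·√[(1 − ρ)/(1 + ρ)]
- baseline-adjusted: δ / √(1 − ρ²) = 0.6·√[2/(1 + ρ)]

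| ρ | δ | group term | group-by-time | baseline-adjusted |
|---|---|---|---|---|
| 0.3 | 0.71 | 54% | 80% | 94% |
| 0.5 | 0.60 | 37% | 80% | 90% |
| 0.7 | 0.46 | 22% | 80% | 86% |
| 0.9 | 0.27 | 10% | 80% | 82% |

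Holding δ at 0.60 instead, group-term power is 42%, 37%, 33% and 30%, against 66%, 80%, 95% and over 99% for group-by-time.

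**The case against.** **The Abstract already ranks the outcomes.** It is the only place that does, no other measure is called a primary outcome, and objective a is purely descriptive, so the Primary objectives heading need not be a list of confirmatory endpoints. This is a fair reading, but the objectives, hypothesis and analysis sections do not follow it. A result on SCIM-III could be defended from the text as primary.

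**The term is implied.** Objectives b and c compare changes, and 90 fits a group-by-time calculation. Both do point that way. But item d does not carry it over, and the fit rests on f = 0.15 and ρ = 0.5, which are not stated. Even with the term settled, the choice between two SCIM measures remains.

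**The correlation is probably high.** Data Collection reports SCIM-SR against SCIM-III correlations above 0.7. These are correlations of scores, and correlations of change may be lower. If they carry over, the two-measure error is at most 8.35% on one term and at most 15.99% on two, so the larger values in step 2 drop out. The error is still above 5%.

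**The fall in group-term power to 10% reflects a shrinking effect.** That stands: δ falls from 0.71 to 0.27 down the table. At a fixed 0.60 SD the group term has 42% to 30%, still well below group-by-time.

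**The two models are nearly one.** With two visits and complete data, the ANOVA interaction and an unconstrained mixed model give essentially the same test. That also stands. They part when week-6 data are missing, and the plan does not say which then decides.

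**ANCOVA is a preference.** Agreed: naming SCIM-SR group-by-time alone would also restore the 5% error. Baseline adjustment is an improvement in precision, not the reason the plan must change. Item d names no site or therapist effect for its mixed model, so ANCOVA discards nothing that was specified.

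**Conclusion.** The concern holds and must be fixed before outcome data are seen. The Abstract and the Primary objectives contradict each other on what is primary, and nothing in the hypothesis, the sample size paragraph or Data Analysis settles the deciding outcome, term or model.

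With the term fixed and either SCIM measure allowed to count, the false-rejection chance is 7.04% to 8.35% for correlations of 0.9 down to 0.7, and up to 9.75% if the tests are independent. With either term also allowed it is 13.58% to 18.55% at equal SDs. All of this assumes two-sided tests and correlations that the documents do not give for the test statistics, but every case examined exceeds 5%. Choosing the group term would also cost more than half of the planned power at ρ = 0.5 (37% against 80%).

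**What to change.** 1. In Data Analysis item d and in the Abstract, replace the two models with one deciding analysis: ANCOVA of the 6-week SCIM-SR total on arm and baseline SCIM-SR total, testing the arm coefficient at two-sided 5% with its 95% CI, each participant analysed in the assigned arm. With one row per participant, no term or covariance structure is left to choose.
2. Move objectives c to e to the Secondary objectives, reported with 95% CIs as supportive.
3. Name SCIM-SR in the null hypothesis and in the Data Collection sentence on testing it, so that no other outcome alone can reject the null.

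**Cost.** Wording only; both SCIM-SR measurements are already planned. The Protocol amendments section requires changes to outcomes and analyses to be communicated to the ethics committee, and the sample size paragraph should then refer to the named test. A positive SCIM-III, religiousness or ADL-domain result becomes supportive only.

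**Limit.** Participants without a 6-week score do not enter the estimate, so ANCOVA does not correct for informative dropout. A mixed model with a common baseline mean and unstructured covariance gives the same estimate when baselines are complete (identical in five simulated datasets with 71 to 84 of 90 followed up), so neither is a missing-data check on the other.

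**Smaller alternative.** Pre-specifying only the SCIM-SR group-by-time term also restores the 5% error, with 80% rather than about 90% power at ρ = 0.5.

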### **Secondary objectives**

- f. To determine the significance of biographical variables (Address zone, Age, Gender, Highest level of Education, Marital status, Employment status, Monthly income, Level of SCI, Type of SCI ‘complete/incomplete’), ASIA, and Dysfunction on the progress of ADL.
- g. To measure the adherence to the intervention using the SADL-eM adherence therapist-report questionnaire which will be developed for this purpose.

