#### **Participants, sampling method, sample size, and setting**

Participants in the study will be SCI inpatients from the Gaza Strip, both genders, of any cause or type of SCI, and age 18-65 years. They will be recruited from admitted inpatients in one of the three rehabilitation settings (Hamad, ElWafa, or ElAmal Rehabilitation hospitals). Readmissions will be included in the study if they are eligible. These three inpatient rehabilitation hospitals are located in the Gaza Strip of Palestine and are private sector health services. They provide comprehensive rehabilitation services. Their rehabilitation teams include physical rehabilitation doctors, rehabilitation nurses, physiotherapists, occupational

therapists, speech therapists, clinical dietitians, psychologists, social workers, orthoptists, and community-based rehabilitation workers. The sample size was determined to detect an effect size of 15%, power of 80%, 5% margin of error, and 95% Confidence Interval (CI). The study sample of 90 SCI individuals will be randomized to two groups, conventional therapy (n1=45) and intervention/SADL-eM & conventional therapy (n2=45) using a simple randomization approach. Inclusion and exclusion criteria are listed in Box 1.

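### The efficacy analysis prespecifies no injury-severity covariates, although ASIA grade, completeness and level are known before randomisation, so precision on SCIM-SR change is forgone at almost no saving

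*Combined protocol and SAP*

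**What the plan says.** The Abstract names the primary outcome: assessment on admission and at six weeks "will use the SCIM-SR as the primary outcome measure". It gives repeated measures ANOVA as the method.

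Data Analysis item d states that "Repeated Measures ANOVA/ Linear Mixed Models will be used will be used to assess differences between intervention and control group using the ADL data". It adds that mixed models cope with missing values and offer fixed and random effects. It lists no model terms. Item c covers the biographical variables, but only as tests at baseline.

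Secondary objective f sets out to establish whether a list of biographical variables matters for ADL progress. The list ends with "Level of SCI, Type of SCI ‘complete/incomplete’), ASIA, and Dysfunction on the progress of ADL". No item in Data Analysis links these variables to ADL progress.

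Under Participants, sampling method, sample size, and setting, patients are allocated "using a simple randomization approach", 45 per arm. No stratification factor is named, and the appended random-number list is a single unstratified draw.

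Box 1 admits ASIA A, B and C, excludes D and E, and excludes complete tetraplegia at C4 or above. Under Data Collection, eligibility is assessed before consent and assignment. Grade, completeness and level must therefore be known before randomisation.

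**The concern.** Severity of injury is handled neither by the design nor by a prespecified model, although the data are collected and the protocol itself asks whether they bear on ADL progress. If ASIA grade and level predict how much SCIM-SR changes over six weeks, that predictable variation is counted as noise and the interval for the arm difference is wider than it need be. Two patients with the same low admission score may differ in recovery if one is ASIA A and the other ASIA C, so adjusting for baseline score alone need not capture this.

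There is also a prespecification issue. With two candidate methods in item d, significance tests at baseline in item c and no covariate list, adjustment could be chosen after results are seen. Writing the list in advance removes that possibility.

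**Working it through.** **Inputs from the documents.** 45 per arm, 80% power, 5% error rate, two visits, SCIM-SR primary.

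**Assumptions.** Two-sided test; equal variance at both visits; within-patient correlation ρ; and R2, the share of within-arm variance in SCIM-SR change explained by ASIA grade and level. The documents give neither ρ nor R2.

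**1. The plan's own figure.** The text reads "The sample size was determined to detect an effect size of 15" per cent, without a scale. It reproduces N=90 if read as Cohen's f = 0.15 for the group-by-time test with ρ = 0.5:

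λ = f² × N × 2/(1−ρ) = 0.0225 × 90 × 2/0.5 = 8.1, on 1 and 88 df, giving power of 80.4%.

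This equals a standardised difference in change of √(4 × 8.1/90) = 0.60. The reading is inferred, not stated. It uses no covariates, so N=90 does not depend on adjustment.

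**2. Power with severity covariates.** With 45 per arm, a t-test has exactly 80% power at d = 0.597 (noncentrality 0.597 × √(45/2) = 2.83, 88 df). Covariates multiply the residual variance by (1−R2). The noncentrality becomes 2.83/√(1−R2), and 3 df are spent, leaving 85. The interval narrows by 1−√(1−R2).

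| Assumed R2 | Noncentrality | Power | Interval narrower by |
|---|---|---|---|
| 0 | 2.83 | 80.0% | 0% |
| 0.05 | 2.91 | 82% | 3% |
| 0.10 | 2.99 | 84% | 5% |
| 0.20 | 3.17 | 88% | 11% |
| 0.30 | 3.39 | 92% | 16% |

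At R2 = 0 the loss is about 0.03 percentage points of power. The group-by-time F test with 4 df spent gives 84.3%, 88.2% and 92.0% at R2 of 0.10, 0.20 and 0.30.

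**3. If baseline SCIM-SR is also a covariate.** The change score has variance 2(1−ρ)σ². Adjusting the six-week score for baseline leaves (1−ρ²)σ². The ratio is (1+ρ)/2, which is 0.75 at ρ = 0.5. The effective d is 0.597/√0.75 = 0.690, and power is about 90%. Dividing d = 0.597 by √(0.75 × (1−R2)), where R2 is now the additional share, gives about 91%, 93% and 95% at 0.05, 0.10 and 0.20.

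**4. Chance imbalance.** With K of 90 patients carrying a factor and 45 per arm, the number X in one arm is hypergeometric and the arm gap is |2X−K|/45.

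| Prevalence (K) | Gap of 15 points or more | Gap of 20 points or more |
|---|---|---|
| 50% (45) | 21% | 9% |
| 33% (30) | 12% | 4% |
| 20% (18) | 6% | 2% |

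This is not an extra loss on top of step 2. The unadjusted variance of the difference, 2σ²/45, splits into R2 × 2σ²/45, which comes from chance imbalance in the covariates, and (1−R2) × 2σ²/45, the remainder. The unadjusted standard error already carries the first part, and adjustment removes it.

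**The case against.** The strongest reply is that the plan is silent here and has not made a bad choice. A reader might infer that the model deliberately excludes severity, or contains only arm and time. The documents do not support that: item d lists no terms, so adjustment is neither prespecified nor ruled out. This stands, and the point is limited to the missing prespecification.

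A reader might also take objective f as saying that these variables are expected to drive recovery. It says only that their significance is to be determined, in one list with address zone, gender, marital status and income. Singling out ASIA grade and level is a statistical judgement, not a ranking found in the protocol.

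Third, the size rests on an R2 that no document supplies. The group-by-time test already removes stable differences between patients, so only severity that predicts change counts. Box 1 narrows the range by excluding ASIA D and E, high complete tetraplegia, ventilated patients and those who become ambulatory during the stay. That may hold R2 down. At 0.05 the gain is only 2 points of power, and baseline adjustment, if adopted, takes part of the available gain. All of this stands and limits the claim.

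It does not remove the case for acting. The covariates are already in hand, and including them costs almost nothing if they prove uninformative.

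**Conclusion.** The point holds as a free improvement. No injury-severity covariate is prespecified and randomisation is unstratified, so any part of SCIM-SR change that severity predicts remains as error. On assumed R2 values of 0.05 to 0.30, the forgone power is about 2 to 12 percentage points from a base of 80%. With baseline SCIM-SR also in the model, at an assumed correlation of 0.5, an additional R2 of 0.05 to 0.20 is worth about 1 to 5 points from a base of about 90%.

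Two stronger conclusions are tempting and should not be drawn. One is that the arm comparison is biased or the sample size wrong: randomisation protects the comparison on average, and N=90 reproduces without covariates under the inferred reading. The other is that a chance severity gap is a second, separate harm: its contribution is already in the unadjusted standard error.

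**What to change.** In Data Analysis item d, name ASIA grade at admission (for example A versus B/C, standing in for complete versus incomplete) and level of injury (tetraplegia versus paraplegia) as fixed covariates in the SCIM-SR and SCIM-III models. They must act on change. In a two-visit model, enter each with its interaction with time, because a main effect alone would not help the group-by-time test. In a baseline-adjusted six-week model, main effects suffice. Fix the list and coding before unblinding, and report the unadjusted model as a sensitivity analysis.

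The cost is a sentence or two of analysis text, notified through the route in Protocol amendments, and two or three degrees of freedom out of 88. No new data, visits or patients are needed. If the factors are not prognostic, the loss of power is negligible.
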